6.2.3 Safety Follow-Up Period

Visit 3: 24-hour after dosing (+/- 2 hours)

Blood sampling could be withheld or reduced per Investigator's judgement, e.g. if limited by blood volume, bleeding and/or distress considerations especially in very young children.

Observations and procedures

- Draw blood 24 hours post-dose for central lab parameters (biomarkers and PK). Record time of blood draw.
- Draw blood 24 hours post-dose for local lab safety evaluation. Record time of blood draw.
- Bleeding assessment for the index bleed (Group A) or any unusual bleed associated with surgery (Group B). Bleeding assessment at or near time of blood draw.
- Surgery/procedure assessment at or near time of blood draw (Group B patients).
- Measure blood pressure and heart rate approximately hourly while the patient is in the emergency department (or similar department), then approximately every 6 to 8 hours for the next 72 hours or until patient is discharged, whichever comes first.
- Record adverse events
- Record concomitant therapies
- Re-start appropriate anticoagulant therapy (at treating physician/Investigator discretion)
- Optional (local) aPTT measurement or other local test

Page 54 of 77

Proprietary confidential information © 2016 Boehringer Ingelheim International GmbH or one or more of its affiliated companies

Visit 4: 7 days after dosing (+/- 3 days)

Observations and procedures

- Bleeding assessment for the index bleed (Group A) or any unusual bleed associated with surgery (Group B).
- Surgery/procedure assessment (Group B patients only).
- Measure blood pressure and heart rate (approximately hourly if the patient is still in the emergency or similar department, then approximately every 6 to 8 hours for the next 72 hours or until patient is discharged), whichever comes first.
- ECG
- Record adverse events
- Record concomitant therapies

Visit 5: End of Trial 30 days after dosing (+ 7 days)

Blood sampling could be withheld or reduced per Investigator's judgement, e.g. if limited by blood volume, bleeding and/or distress considerations especially in very young children.

Observations and procedures:

- Bleeding assessment for the index bleed (Group A) or any unusual bleed associated with surgery (Group B). Bleeding assessment at or near time of blood draw.
- Surgery/procedure assessment at or near time of blood draw (Group B patients only).
- Measure blood pressure and heart rate
- Draw blood for central lab parameters (ADA). Record time of blood draw.

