10.3 ESTIMATED TOTAL BLOOD VOLUME

The estimated Total Blood Volume (TBV) will depend on age and gender and will be calculated with following formula:

Total Blood Volume = Weight * Average Blood Volume

Table 10.3.1:Approximate (average) blood volume per age category.

Age category	Approximate (average) blood volume (mL/Kg)
Term newborn infant	80 - 90 (85)
Infants	80
Children (> 3 months)	70-80
Adolescents	
women	65
men	75

For children the approximate total blood volume may vary between 70 - 80 mL/Kg. In order to be conservative, 70 mL/Kg will be used to calculate the total blood volume (TBV).

Examples of TBV calculations:

Infant of 1.5 year old, weight 10 Kg:

- Allowed blood loss at any single time (1% of TBV): 8 mL
- Allowed blood loss over four weeks (3% of TBV): 24 mL

Child of 12 years old, weight 45 Kg:

- Allowed blood loss at any single time (1% of TBV): 31.5 mL
- Allowed blood loss over four weeks (3% of TBV): 94.5 mL

Adolescent (male) of 15 years old, weight 60 Kg:

- Allowed blood loss at any single time (1% of TBV): 45 mL
- Allowed blood loss over four weeks (3% of TBV): 135 mL

Blood sampling could be withheld or reduced per Investigator's judgement, e.g. if limited by blood volume, bleeding and/or distress considerations especially in very young children.

If blood sampling is reduced, central lab parameters will be analysed in a priority order as indicated below:

- 1) Sum dabigatran pre-dose (baseline)
- 2) All coagulation biomarkers pre-dose, 30 minutes and 24 hours post-dose
- 3) Idarucizumab ADA pre-dose and 30 days post-dose
- 4) PK idarucizumab at time points pre-dose; 30 minutes and 24 hours post-dose
- 5) All coagulation biomarkers at time points prior vial 2, 4 hours and 12 hours post-dose
- 6) PK idarucizumab at time points prior vial 2, 4 hours and 12 hours post-dose

Boehringer Ingelhein	1	4 February 2016
BI Trial No.: 1321.7		
c08884404-01	Trial Protocol	Page 73 of 77
D		0.1. 0011 1

7) Unbound sum dabigatran at all time points as noted in Flow Chart

In below tables a few scenarios are displayed if collected blood volumes are limited.

Table 10.3: 1Reduced blood draw schedule (patients < 6 years of age):
Maximal 29 mL central lab/local safety blood draw (e.g. no EDTA blood
collection prior vial 2, 4 hours and 12 hours post-dose; i.e. no measurement of
unbound sum dabigatran and no PK idarucizumab prior vial 2, 4 hours and 12
hours post-dose)

		Time	EDTA	Na Citrate	Local Safety Lab	Total blood volume

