Visit 1	1	Screening	11111		$\sim 2 \text{ to } 6 \text{ mL}$	~ 2 to 6 mL
Visit 2.1	2	Baseline (just prior vial 1)	2.7 mL	1.4 mL		4.1 mL
		Admini	ster Idaruciz	zumab Vial	1	
Visit 2.2	3	Just prior vial 2		1.4 mL		1.4 mL
	•	Admini	ster Idaruciz	zumab Vial	2	
Visit 2.2	4	30 minutes $(\pm 10 \text{ minutes})$	2.7 mL	1.4 mL		4.1 mL
	5	4 hours (± 30 minutes)		1.4 mL		1.4 mL
	6	12 hours (± 1 hour)		1.4 mL		1.4 mL
Visit 3	7	$\begin{array}{c} 24 \text{ hours} \\ (\pm 2 \text{ hours}) \end{array}$	2.7 mL	1.4 mL	~ 2 to 6 mL	~ 6 to 10 mL
Visit 4	8	Day 7 (± 3 days)				
Visit 5	9	Day 30 (+ 7 days)	1.2 mL			1.2 mL
Total blood	Total blood volume					~21 to 29 mL

Boehringer Ingelheim		4 February 2016
BI Trial No.: 1321.7		
c08884404-01	Trial Protocol	Page 74 of 77
		C' CC'1' 1 '

Table 10.3: 2Reduced blood draw schedule (patients < 6 years of age):	Maximal **25 mL** central lab/local safety blood draw (e.g. no blood collection prior vial 2, 4 hours and 12 hours post-dose; i.e. no measurement of biomarkers, unbound sum dabigatran and no PK idarucizumab prior vial 2, 4 hours and 12 hours post-dose)

		Time	EDTA	Na Citrate	Local Safety Lab	Total blood volume
Visit 1	1	Screening			~ 2 to 6 mL	~ 2 to 6 mL
Visit 2.1	2	Baseline (just prior vial 1)	2.7 mL	1.4 mL		4.1 mL
		Admini	ster Idaruciz	zumab Vial	1	
Visit 2.2	3	Just prior vial 2				
		Admini	ster Idaruciz	zumab Vial	2	
Visit 2.2	4	30 minutes (± 10 minutes)	2.7 mL	1.4 mL		4.1 mL
	5	4 hours (± 30 minutes)				
	6	12 hours $(\pm 1 \text{ hour})$				
Visit 3	7	$\begin{array}{c} 24 \text{ hours} \\ (\pm 2 \text{ hours}) \end{array}$	2.7 mL	1.4 mL	~ 2 to 6 mL	~ 6 to 10 mL
Visit 4	8	Day 7 (± 3 days)				
Visit 5	9	Day 30 (+ 7 days)	1.2 mL			1.2 mL
Total blood volume					~17 to 25 mL	

Boehringer Ingelheim		4 February 2016
BI Trial No.: 1321.7		
c08884404-01	Trial Protocol	Page 75 of 77
		C'1 CC1' 1 1

Table 10.3: 3 Reduced blood draw schedule (patients \geq 6 years of age):

Maximal **40 mL** central lab/local safety blood draw (e.g. no EDTA blood collection prior vial 2, 4 hours and 12 hours post-dose; i.e. no measurement of unbound sum dabigatran and no PK idarucizumab prior vial 2, 4 hours and 12 hours post-dose)

		Time	EDTA	Na Citrate	Local Safety Lab	Total blood volume
Visit 1	1	Screening			~ 3 to 6 mL	~ 3 to 6 mL
Visit 2.1	2	Baseline (just prior vial 1)	3.0 mL	2.7 mL		5.7 mL
		Admini	ster Idaruciz	umab Vial 1	l	
Visit 2.2	3	Just prior vial 2		2.7 mL		2.7 mL
		Admini	ster Idaruciz	zumab Vial 2	2	

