Visit 2.2	4	30 minutes (± 10 minutes)	3.0 mL	2.7 mL		5.7 mL
	5	4 hours (± 30 minutes)		2.7 mL		2.7 mL
	6	12 hours (± 1 hour)		2.7 mL		2.7 mL
Visit 3	7	24 hours (± 2 hours)	3.0 mL	2.7 mL	~ 3 to 6 mL	~ 9 to 12 mL
Visit 4	8	Day 7 (± 3 days)				
Visit 5	9	Day 30 (+ 7 days)	3.0 mL			3.0 mL
Total blood	Total blood volume					~ 34 to 40 mL

Boehringer Ingelheim		4 February 2016
BI Trial No.: 1321.7		
c08884404-01	Trial Protocol	Page 76 of 77
		C'4 CC1' 4 1

Table 10.3: 4 Reduced blood draw schedule (patients \geq 6 years of age):

Maximal **32 mL** central lab/local safety blood draw (e.g. no blood collection prior vial 2, 4 hours and 12 hours post-dose; i.e. no measurement of biomarkers, unbound sum dabigatran and no PK idarucizumab prior vial 2, 4 hours and 12 hours post-dose)

		Time	EDTA	Na Citrate	Local Safety Lab	Total blood volume
Visit 1	1	Screening			~ 3 to 6 mL	~ 3 to 6 mL
Visit 2.1	2	Baseline (just prior vial 1)	3.0 mL	2.7 mL		5.7 mL
		Admini	ster Idaruciz	zumab Vial 1	l	
Visit 2.2	3	Just prior vial 2				
		Admini	ster Idaruciz	zumab Vial 2	2	
Visit 2.2	4	30 minutes (± 10 minutes)	3.0 mL	2.7 mL		5.7 mL
	5	4 hours (± 30 minutes)				
	6	12 hours (± 1 hour)				
Visit 3	7	24 hours $(\pm 2 \text{ hours})$	3.0 mL	2.7 mL	~ 3 to 6 mL	~ 9 to 12 mL
Visit 4	8	Day 7 (± 3 days)				
Visit 5	9	Day 30 (+ 7 days)	3.0 mL			3.0 mL
Total blood v	Total blood volume					~26 to 32 mL

Page 77 of 77

Proprietary confidential information © 2016 Boehringer Ingelheim International GmbH or one or more of its affiliated companies

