#### 5.2.2 Other Secondary endpoints

- Percent change of coagulation tests (dTT and ECT) at 30 minutes post-dose compared to pre-dose.
- Time to achieve complete reversal of dabigatran effect, based on coagulation tests (dTT and ECT).
- Duration of complete reversal of dabigatran effect sustained at 24 hours post-dose, based on coagulation tests (dTT and ECT).
- Cessation of bleeding (Group A patients only).
- Bleeding status and other clinical conditions that may contribute to bleeding (Group A patients only) during the trial.
- Development of treatment-emergent ADA with cross reactivity to idarucizumab at 30 days post-dose of idarucizumab.

 TSAP for BI Trial No: 1321.7
 Page 9 of 20

 Proprietary confidential information © 2017 Boehringer Ingelheim International GmbH or one or more of its affiliated companies

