#### 6.6 HANDLING OF MISSING DATA AND OUTLIERS

With respect to efficacy and safety evaluations, it is not planned to impute missing values. The reversal of anticoagulation cannot be defined if either the pre-dose or all post-dose coagulation test is missing, or if the pre-dose coagulation test is below the ULN. Patients in such case will be considered as not evaluable for the corresponding biomarker.

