#### Boehringer Ingelheim TSAP for BI Trial No: 1321.7

Proprietary confidential information © 2017 Boehringer Ingelheim International GmbH or one or more of its affiliated companies

Missing or incomplete AE dates will be imputed according to BI standards (see "Handling of missing and incomplete AE dates") (2).

Handling of missing PK data will generally be performed according to the BI standards (3).

Drug concentration data identified with below the lower limit of quantification (BLQ) will be displayed as such and not replaced by zero at any time point (this rule also applies to the lag phase, including the pre-dose values) with the exception of unbound sum dabigatran. For this analyte, data identified with BLQ following the administration of idarucizumab may be replaced with the lower limit of quantification, until measurable concentrations re-occur.

The appropriate time frame will be decided by the Trial Clinical Pharmacokineticist (TCPK) and described in the CTR.

With respect to pharmacodynamic evaluations it is not planned to impute missing values. However, clotting times may exceed the maximum clotting time of 500s recorded by the coagulometer, indicating the presence of high concentrations of dabigatran, for example in pre-dose idarucizumab samples. If the blood clotting time exceeds 500s, above the upper limit of quantification (ALQ) will be reported. For calculation of reversal of the anticoagulation effect, ALQ values may be replaced by 500s. In that case ALQ values will be discussed on an individual basis within the trial team (including TCM, Trial Biomarker Analyst (TBMA), TCPK and Trial Statistician (TSTAT) and decisions will be documented in the CTR. There are no rules for evaluation. BLQ values as well as pharmacodynamic data identified with no sample available (NOS), no valid result (NOR), and not analysed (NOA) will not be considered.

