#### 7.5.2 Other Secondary endpoints

Percent change from baseline of coagulation tests (dTT and ECT) at 30 minutes post-dose will be summarized descriptively or listed only if deemed appropriate.

Reversal of the anticoagulant effect of dabigatran at time t is defined as:

$$Reversal (t) = \frac{predose coagulation test - postdose coagulation test at time t}{predose coagulation test - ULN} \times 100\%$$

Values equal to or higher than 100% will be interpreted as complete reversal of the anticoagulant effect. The reversal of anticoagulant activity will be based on central lab measurements and calculated for coagulation tests, dTT and ECT, separately. Reversal cannot be defined for patients with dTT or ECT pre-dose measurement value less than ULN; such patients are considered as not evaluable for reversal related endpoints. The ULN was determined by using data from studies 1321.1 and 1321.2, calculated as the (arithmetic) mean +2 \* standard deviation (SD) by using all data collected prior to the dosing of dabigatran and the data from patients who were on placebo, as well as pre-dose data from idarucizumab alone treatment (as available).

Time to achieve complete reversal will be reported by listing the calculated reversal values at planned time points and using flags to show whether complete reversal is achieved at planned time points.

Duration of complete reversal, defined as the time period from when a patient first achieves complete reversal, up to the earliest time point among the following: middle point between last observation of 100% reversal and subsequent observation, 24 hours post-dose or re-

starting the treatment of dabigatran or other anticoagulation. Duration of complete reversal can be defined only for those patients who achieved complete reversal.

For Group A patients only, the cessation of bleeding within 24 hours will be reported in a listing.

For Group A patients only, bleeding status will be assessed during treatment period and be summarized descriptively or listed only if deemed appropriate. Other clinical conditions that may contribute to bleeding (Group A patients only) during the trial, such as major trauma or the use of antiplatelets, will also be reported.

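### The SAP's duration-of-reversal rule has no censoring, so a missing late sample is credited as complete reversal to 24 h

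*SAP*

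**What the plan says.** SAP 7.5.2 starts the duration at first complete reversal (a reversal value of 100% or more). It ends it at the earliest of the "middle point between last observation of 100% reversal and subsequent observation, 24 hours post-dose", or restart of dabigatran or another anticoagulant. The one condition it attaches to duration itself is that complete reversal was achieved.

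On missing data, SAP 6.6 says "it is not planned to impute missing values". It makes reversal undefined only when the pre-dose test or all post-dose tests are missing, or when the pre-dose value is below the ULN. It adds that "pharmacodynamic data identified with no sample available (NOS), no valid result (NOR), and not analysed (NOA) will not be considered". Neither SAP 6.6, SAP 7.5.2 nor Protocol 7.5 mentions censoring, or says what happens to duration when no sample follows the last complete one.

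The protocol expects sampling to be withheld or reduced in some children. Protocol 10.3 includes a 25 mL schedule (under 6 years) and a 32 mL schedule (6 years and over) with "no blood collection prior vial 2, 4 hours and 12 hours post-dose". In both, the 24 h draw is the only biomarker sample after 30 minutes. That draw is well protected: "All coagulation biomarkers pre-dose, 30 minutes and 24 hours post-dose" stands second of seven in the priority order, and all four reduced schedules keep it.

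**The concern.** Without a later evaluable sample no midpoint can be formed, and the earliest remaining stop is 24 h (or restart, if that comes first). A withheld draw, an invalid result, withdrawal and death all lead there. Read literally, a death before 24 h would even leave reversal time counted after death.

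In effect the rule fills in unobserved time as complete reversal, which fits poorly with the no-imputation statement in SAP 6.6. The ordering is also wrong: no result scores the same as the best result and better than a measured loss. Persistence should not be assumed. In the adult interim data in Protocol 1.1, the share of patients with unbound sum dabigatran below 20 ng/mL fell from 93% at 12 h to 79% at 24 h. Those are concentrations in adults, not clotting-test reversal in children, but they concern the interval that the rule fills in.

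A secondary point depends on reading the last complete observation as the last in the whole record. A loss that is later regained is then ignored, although the endpoint in SAP 5.2.2 is "Duration of complete reversal of dabigatran effect sustained at 24 hours post-dose".

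**Working it through.** The documents give no duration figure to reproduce, so the rule was applied as written.

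**Inputs**
- Post-dose biomarker samples at 0.5, 4, 12 and 24 h (Protocol 6.2.2 and 6.2.3). The 24 h visit has a window of ± 2 h.
- 25 mL and 32 mL schedules: 0.5 and 24 h only (Protocol 10.3).
- Results without a value are set aside (SAP 6.6), so they cannot serve as a later observation.
- Assumptions: first complete reversal at 0.5 h, nominal times unless stated, no restart before 24 h.

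**Formula**

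Duration = min(24, midpoint of last complete and next evaluable sample if one exists) − first complete.

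Observed support = last complete − first complete. This takes reversal as continuous between complete samples.

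C = complete, L = lost, – = no evaluable result.

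| Schedule (h) | Pattern | Duration under SAP 7.5.2 | Observed support |
|---|---|---|---|
| 0.5/4/12/24 | CCCC | 24 − 0.5 = 23.5 h | 23.5 h |
| 0.5/4/12/24 | CCC– | 24 − 0.5 = 23.5 h | 12 − 0.5 = 11.5 h |
| 0.5/4/12/24 | CCCL | (12 + 24)/2 − 0.5 = 17.5 h | 11.5 h |
| 0.5/4/12/24 | CC–– | 24 − 0.5 = 23.5 h | 4 − 0.5 = 3.5 h |
| 0.5/4/12/24 | C––– | 24 − 0.5 = 23.5 h | 0 h |
| 0.5/24 | CC | 24 − 0.5 = 23.5 h | 23.5 h |
| 0.5/24 | C– | 24 − 0.5 = 23.5 h | 0 h |
| 0.5/24 | CL | (0.5 + 24)/2 − 0.5 = 11.75 h | 0 h |

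**Missing result against measured loss**
- Full schedule: 23.5 − 17.5 = 6 h longer for the missing result.
- Reduced schedules: 23.5 − 11.75 = 11.75 h longer, a ratio of 2.

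**Sensitivity to the 24 h window**
- Full schedule, loss measured at 22 h: (12 + 22)/2 − 0.5 = 16.5 h; at 26 h: (12 + 26)/2 − 0.5 = 18.5 h.
- Reduced schedules, loss measured at 22 h: (0.5 + 22)/2 − 0.5 = 10.75 h; at 26 h: (0.5 + 26)/2 − 0.5 = 12.75 h.

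All four stay below the 23.5 h given to a missing result.

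**Restart before 24 h.** With restart at 10 h and only the 0.5 h sample evaluable, the rule gives 10 − 0.5 = 9.5 h, again with 0 h of observed support.

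**Secondary point.** For C, L, C, C the whole-record reading gives 24 − 0.5 = 23.5 h. Stopping at the first loss gives (0.5 + 4)/2 − 0.5 = 1.75 h.

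**The case against.** The strongest reply is that the SAP is silent on this case rather than wrong. If the midpoint cannot be formed, duration could be taken as undefined, and the no-imputation statement could be read as forbidding reversal to be carried forward. But SAP 7.5.2 asks for the earliest of the listed points, and 24 h is always available. The only undefined case it names for duration is failure to achieve complete reversal. The further evaluability conditions (pre-dose value at or above the ULN, a pre-dose and at least one post-dose result) are already met by anyone with a complete value. SAP 6.6 conflicts with the outcome but gives no instruction that changes it.

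The published SAP skips some section numbers (6.4, 7.6 and 9), so a rule in withheld text cannot be excluded. The finding is limited to the text available.

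The objections about impact largely stand. There are about 5 patients and no inference, SAP 7.5 plans to list the secondary endpoints, and a listing of reversal values lets a reader see a missing 24 h result. The case also needs that protected sample to be lost, with no earlier restart. Still, Protocol 7.3.2 reports both time to and duration of reversal through listed values and flags. The SAP attaches the flags to time to reversal and gives duration a derived number, which would carry no censoring mark.

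The secondary point is weaker. The word sustained could mean status at 24 h, which the pattern C, L, C, C satisfies.

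**Conclusion.** The concern holds. As written, the rule can report up to 23.5 h of complete reversal with no observed support beyond the first complete sample. It scores a missing 24 h result 6 h longer than a measured loss under the full schedule, and 11.75 h longer (double) under the 25 mL and 32 mL schedules. The error can only lengthen the reported duration.

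These figures rest on first complete reversal at 0.5 h, nominal times and no restart before 24 h. An earlier start would lengthen every duration equally and leave the hour differences unchanged. The documents give no rate of missing 24 h results, so no frequency is claimed. The practical effect is limited by the descriptive, listed reporting, but with about 5 patients one wrong value is a large share of the listing, so the SAP should be corrected. The loss-then-regain question is a request for clarity and does not carry the conclusion.

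**What to change.** Amend SAP 7.5.2 as follows:

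- When no evaluable sample follows the last complete one, censor at that sample, or at restart of anticoagulation if earlier, and print the duration as ≥ x h. State that this also covers withdrawal and death before 24 h.
- Treat a complete sample within the 24 h window (± 2 h) as reaching 24 h and list its actual time. This extends at most 2 h past the sample.
- Keep 24 h and restart as upper bounds.
- State whether the first observed loss ends the period, and list any re-attainment separately so that both values are visible.

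On the examples above, CCC– becomes ≥ 11.5 h, CC–– becomes ≥ 3.5 h, and a patient with only the 0.5 h result becomes ≥ 0 h. Patients who are complete throughout, or who have a measured loss with no later recovery, keep their values.

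The cost is a few SAP sentences and a changed derivation program, with no new data. Some durations will become shorter or be shown as censored.

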7.3.2 Secondary endpoint analyses

Percent change from baseline of coagulation tests (dTT and ECT) at 30 minutes post-dose will be summarized descriptively.

Time to achieve complete reversal and duration of complete reversal of dabigatran effects sustained at 24 hours post-dose based on coagulation tests (dTT and ECT) will be reported by listing the reversal values at planned time points and using flags to show whether complete reversal is achieved.

For Group A patients only, the cessation of bleeding will be reported using a binary outcome (Yes/No) descriptively.

Bleeding status and other clinical conditions that may contribute to bleeding (Group A patients only) during the trial will be reported descriptively.

Development of treatment-emergent ADA with cross reactivity to idarucizumab at 30 days post-dose of idarucizumab will be summarized using a binary outcome (Yes/No) descriptively.

Page 57 of 77

Proprietary confidential information © 2016 Boehringer Ingelheim International GmbH or one or more of its affiliated companies

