### 4. CHANGES IN THE PLANNED ANALYSIS OF THE STUDY

Sample size is estimated to be approximately 5 patients. Depending on the actual sample size, listings only may be provided while the descriptive summaries specified in the protocol may not be displayed.

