#### 6. GENERAL ANALYSIS DEFINITIONS

#### 6.1 **TREATMENT**

It is planned to include approximately 5 patients in this trial. All patients will receive idarucizumab (short label: Ida), which will be administered intravenously as two equal consecutive infusions over 5 to 10 minutes each or as two bolus injections no more than 15 minutes apart.

The residual effect period (REP) is defined as 1 day after the last trial medication application. The following treatment period will be defined:

- Screening: day of informed consent to day of first idarucizumab administration. If same day, then the period before first vial administration of idarucizumab.
- On-treatment: time of first administration of idarucizumab to time of last administration of idarucizumab + 1 day.
- Post-treatment: time after last idarucizumab administration + 1 day, to day of end of trial visit (Visit 5) or consent withdraw.

As it may take up to 5 days for some potentially drug related reactions to show up, 5-day REP will also be considered as sensitivity analysis.

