#### 10. **HISTORY TABLE**

Table 10: 1 History table

Version	Date (DD-MMM-YY)	Author	Sections changed	Brief description of change
Initial	22-JUL-16		None	This is the initial TSAP with necessary information for trial conduct. This initial TSAP is based on the protocol finalized on 04Feb2016.
Final	31-JUL-17		None	This is the final TSAP without any modification. This final TSAP is based on the protocol finalized on 04Feb2016. Changes to the planned analysis are summarized in Section 4 and detailed in the corresponding sections of the SEAP.

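### SAP 7.5.2 cuts Group A bleeding status to the treatment period and bleeding cessation to 24 hours, against endpoint definitions without those limits, and SAP section 4 does not declare it

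*SAP*

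**What the plan says.** The endpoint list in SAP section 5.2.2 matches protocol section 5.1.2. Cessation of bleeding in Group A carries no time limit. The companion endpoint is "Bleeding status and other clinical conditions that may contribute to bleeding (Group A patients only) during the trial". Footnote b of protocol 5.1.2 marks both as safety issues.

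Protocol section 7.3.2 plans the analysis on the same terms. For Group A, "the cessation of bleeding will be reported using a binary outcome (Yes/No) descriptively", and bleeding status is reported together with contributing conditions over the trial.

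SAP section 7.5.2 differs. On cessation, "the cessation of bleeding within 24 hours will be reported in a listing". On the second endpoint, "bleeding status will be assessed during treatment period and be summarized descriptively or listed only if deemed appropriate". The next sentence returns to the full period for the other half of that endpoint, the conditions that "may contribute to bleeding (Group A patients only) during the trial, such as major trauma".

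SAP section 4 declares one change: "listings only may be provided while the descriptive summaries specified in the protocol may not be displayed". The history table in SAP section 10 states: "Changes to the planned analysis are summarized in Section 4".

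**The concern.** The analysis text covers less time than the endpoints it is meant to analyse, and a reader of SAP section 4 would not know.

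What is lost is the later course of the index bleed: whether it stayed stopped, and whether a bleed still present at 24 hours stopped afterwards. That period is informative by the protocol's own account. The Flow Chart places any restart of anticoagulation at Visit 3. Protocol section 1.1 reports that, in adults, the share with unbound dabigatran below 20 ng/mL fell from 93% at 12 hours to 79% at 24 hours.

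Protocol section 1.1 expects two or three bleeds needing urgent intervention across the two parent trials, and possibly far fewer. With no inference planned, each Group A child's listed course is the result.

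**Working it through.** No hypothesis is tested and the sample size is set by feasibility, so there is no planned figure to reproduce. The check compares texts and counts scheduled assessments.

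**Step 1: definitions against analysis.**

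| Endpoint | Protocol 5.1.2, 7.3.2; SAP 5.2.2 | SAP 7.5.2 | Declared in SAP 4? |
|---|---|---|---|
| Bleeding status | whole trial | treatment period | no |
| Contributing conditions | whole trial | whole trial | no change |
| Cessation of bleeding | no time limit | 24 hours, start point not given | no |

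SAP section 4 covers the move from summary to listing. It does not cover a change of time window.

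**Step 2: what treatment period can mean.** Two meanings are available.
- The SAP section 6.1 period: "On-treatment: time of first administration of idarucizumab to time of last administration of idarucizumab + 1 day". Protocol section 7.3.4 and SAP section 7.8.1 end the treatment period at the same point for adverse events.
- The Flow Chart Treatment Period, which is Visits 2.1 and 2.2. Visits 3, 4 and 5 stand under Safety Follow-Up.

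SAP section 6.1 also mentions a 5-day residual effect period as a sensitivity analysis. It ties this to drug-related reactions, not to bleeding status.

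**Step 3: scheduled bleeding assessments after dosing is complete.** Protocol sections 6.2.2 and 6.2.3 place them at or near the blood draws of Visit 2.2 and at Visits 3, 4 and 5: 3 + 1 + 1 + 1 = 6.

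| Assessment | SAP 6.1 on-treatment | Flow Chart Treatment Period |
|---|---|---|
| 30 min, 4 h, 12 h (Visit 2.2) | in | in |
| 24 h ± 2 h (Visit 3) | in only if by 24 h | out |
| Day 7 ± 3 days (Visit 4) | out | out |
| Day 30 + 7 days (Visit 5) | out | out |

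- SAP 6.1 meaning: 2/6 = 33% out, or 3/6 = 50% if Visit 3 takes place after 24 hours.
- Flow Chart meaning: 3/6 = 50% out.
- If the assessment at the draw before vial 2 is counted as well, the shares are 2/7 = 29% and 3/7 = 43%.

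In every case Day 7 and Day 30 are out.

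**Step 4: the 24-hour cut-off for cessation.** The Visit 3 window is 24 − 2 = 22 to 24 + 2 = 26 hours, so the visit that would show whether bleeding had stopped by 24 hours can fall on either side of the limit. The start of the clock is unstated, but this is a small matter. Under protocol section 4.1.4, two parts of at most 15 minutes with a gap of at most 15 minutes give 15 + 15 + 15 = 45 minutes.

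**Step 5: whether another analysis covers the gap.** SAP section 7.2 lists the baseline bleeding assessment only. SAP section 7.8.5, for other safety data, is marked not applicable. SAP section 7.8.1 lists all adverse events, including post-treatment ones, but protocol section 5.3.6.2 has the index bleed captured as a serious adverse event in the parent trial and treats abnormalities present before inclusion as baseline conditions. A re-bleed recorded as an adverse event would appear. An unworsened index bleed that stops on, say, Day 3 need not. No adverse event listing confirms that bleeding stayed stopped.

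**The case against.** **SAP 6.1 can be read more widely.** It introduces screening, on-treatment and post-treatment together under the words treatment period, and post-treatment runs to Visit 5. On that reading nothing is lost. This does not survive SAP 7.8.1, which names treatment and post-treatment as separate periods, or protocol 7.3.4. It does show that the term needs defining.

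**SAP 7.5 promises to list the secondary endpoints.** It does, but the specific rule in 7.5.2 governs how this one is reported.

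**The 24-hour limit is elaboration.** A Yes/No outcome needs a time point, the protocol gives none, and 24 hours matches the reversal-duration endpoint. This has force, and the cessation half is the weaker one. Even so, the limit drops later cessation from an endpoint that included it, and it is not declared.

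**Adverse event collection covers most of the harm.** All adverse events are collected to Visit 5, worsening of a pre-existing condition must be recorded, and protocol section 3.1 has events recorded in both trials. This holds for re-bleeds and worsening. It leaves the persistent, unworsened index bleed and the confirmation of lasting cessation.

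**The percentages are crude.** A 30-minute check and a Day 30 check count equally, and the denominator can be argued. That is fair; the conclusion rests on which visits are left out.

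**Some sections are not in the public text.** The protocol's further-endpoints section is among them. Later bleeding might be reported there, but that would not remove a contradiction in a visible secondary endpoint.

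**Conclusion.** The concern holds. SAP 7.5.2 contradicts SAP 5.2.2 and protocol sections 5.1.2 and 7.3.2 on bleeding status, and it adds an undeclared limit to cessation. Followed as written, it leaves the Day 7 and Day 30 index-bleed assessments without a planned analysis under this endpoint, and possibly the 24-hour assessment too: 2 or 3 of 6.

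The bleeding-status conflict is certain from the text. The practical loss rests on two assumptions: that treatment period has one of the two meanings in step 2, and that no unseen section reports later bleeding. The primary endpoint is unaffected and there is no inference to distort. What suffers is the completeness of a safety-marked endpoint in a very small case series. It should be corrected.

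**What to change.** In SAP section 7.5.2:

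1. Report Group A bleeding status at every scheduled assessment through Visit 5, in place of the treatment-period limit.
2. List cessation whenever it occurs, with its time counted from a stated vial and a flag for cessation within 24 hours. Show later assessments in the same listing so that any recurrence is visible.
3. If either restriction is intended, define the window in SAP section 5.2.2 and declare it with the reason in SAP section 4.

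The adverse event windows in SAP section 7.8.1 can stay as they are.

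The cost is SAP wording and a few columns in a listing of about 5 patients. The assessments are already scheduled through Visit 5. The documents do not show whether the clock time of cessation is recorded. If it is not, list the first assessment at which bleeding has stopped.
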